6.1. Populations for Analyses

For purposes of analysis, [Table GPHD.6.1](#) defines the following analysis populations/data sets.

Table GPHD.6.1. Analysis Populations/Data Sets

| Population/Data Set | Description |
|---|--|
| Screened population | All participants who sign informed consent |
| Enrolled population | All participants who are exposed to at least 1 dose of insulin glargine (U100) after Visit 2 |
| Randomized population | All participants who are randomly assigned a treatment arm |
| Safety Population | All randomly assigned participants who are exposed to at least 1 dose of study drug (tirzepatide or insulin lispro [U100]). |
| Modified intention-to-treat (mITT) population | All randomly assigned participants who are exposed to at least 1 dose of study drug (tirzepatide or insulin lispro [U100]), excluding inadvertently enrolled participants who have discontinued study drug for that reason. |
| Lead-in analysis set (LAS) | Data obtained during Study Period I, after first dose of insulin glargine (U100) after Visit 2 and prior to the first dose of tirzepatide or insulin lispro (U100) (or Visit 6 date if the dose date is missing). |
| Efficacy analysis set (EAS) | Data obtained during Study Period II from the mITT population, excluding data after initiating rescue antihyperglycemic medication or early discontinuation of study drug (tirzepatide: last dose date + 7 days; insulin lispro (U100): last dose date). |
| Full analysis set (FAS) | All available data obtained during Study Period II, regardless of adherence to study drug or initiation of rescue antihyperglycemic medication. |
| Safety analysis set (SS) | All available data obtained during Study Periods II and III regardless of adherence to study drug or initiation of new antihyperglycemic medication. |

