6.13. Safety Analyses

Unless specified otherwise, safety assessments will be based on the Safety analysis Set (see [Table GPHD.6.1](#)). All events that occur between the date of first dose of study drug (ie, tirzepatide or insulin lispro [U100]) to the date of the patient's safety follow-up visit or the patient's end of study participation will be included, regardless of the adherence to study drug or initiation of rescue therapy. For assessing the benefit- risk profile through 52 weeks, selected safety analyses will be conducted by utilizing safety data from first dose through the date of the 52-week visit. Some safety analyses may be conducted after excluding data after initiation of new antihyperglycemic therapy. Additional safety analyses may be conducted using the LAS data set.

Unless specified otherwise, statistical assessment of homogeneity of the distribution of categorical safety responses among treatment arms (pooled cohort of tirzepatide doses and insulin lispro) will be conducted using Fisher exact test.

Unless specified otherwise, differences among treatment mean changes from baseline in continuous safety parameters at all scheduled visits will be assessed via an MMRM using REML. The model will include treatment, visit, treatment-by-visit interaction, country/pooled country, baseline HbA1c ($\leq 8.5\%$, $>8.5\% [\leq 69, >69 \text{ mmol/mol}]$), and baseline metformin use (Yes/No) as fixed effects, and baseline value of the safety parameter as a covariate. To model the covariance structure within patients, the unstructured covariance matrix will be used. If this model fails to converge, the covariance structures specified in Section [6.12.1.1](#) will be tested in order.

Unless specified otherwise, statistical summaries and analyses of safety assessments will be displayed in the following treatment order: individual tirzepatide doses (5 mg, 10 mg, 15 mg), pooled cohort of tirzepatide doses and insulin lispro (U100).

For selected safety parameters, time-to-first-event analysis via the Cox proportional hazards model may be conducted. For patients without an event, the “time-to-event” will be time (in days) from first dose to end of study participation. For patients experiencing the event, “time-to-first-event” will be the time (in days) from first dose to first occurrence of the event.

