Where necessary, the rate of events will be analyzed using a generalized linear mixed-effects model assuming the number of events follow a negative binomial distribution, and including treatment as a fixed effect. The logarithm of days during the active treatment period will be adjusted as an offset to account for possible unequal treatment duration of follow-up between patients.

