For selected categories of hypoglycemia (including severe hypoglycemia and level 2 hypoglycemia/severe hypoglycemia), statistical summaries and analyses will exclude hypoglycemic events occurring after initiation of a new antihyperglycemic therapy. Incidence as well as rate per year of exposure will be provided by treatment.

Statistical summaries and analyses for severe hypoglycemia requiring hospitalization, documented medical help or is life threatening will be conducted using the Safety Analysis Set.

The incidence of hypoglycemic event will be analyzed using logistic regression with treatment, baseline HbA1c category, country/pooled country, and baseline metformin use (Yes/No) as fixed effects. The baseline incidence of hypoglycemic event during the insulin glargine (U100) optimization period and insulin optimization group may be adjusted as fixed effects. The rate of hypoglycemic episodes per patient year may be analyzed using a generalized linear mixed-effects model assuming the number of hypoglycemic episodes follows a negative binomial distribution with the mean modeled using country/pooled country, baseline metformin use (Yes/No), baseline HbA1c category, and treatment as fixed effects. The logarithm of days during the active treatment period will be adjusted as an offset to account for possible unequal treatment duration of follow-up between patients. The treatment term will include the combined tirzepatide arm and insulin lispro (U100). The baseline incidence/rate of hypoglycemic event during the

lead-in period and insulin optimization group may be adjusted as fixed effects. A nonparametric empirical model may be used to analyze the rate of hypoglycemic episodes if the event rate is low.

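### The offset in the event-rate models is an undefined 'active treatment period' that does not match the window in which events are counted, so the rates are biased under either ordinary reading

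*SAP*

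**What the plan says.** **Default counting window.** SAP 6.13 starts at first dose and runs to the safety follow-up visit or the end of participation. Events up to the patient's "end of study participation will be included, regardless of the adherence to study drug or initiation of rescue therapy". SAP 6.1 defines the safety analysis set to match: "All available data obtained during Study Periods II and III regardless of adherence to study drug or initiation of new antihyperglycemic medication".

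**Narrower window for some hypoglycemia categories.** For selected categories, including severe and level 2/severe hypoglycemia, SAP 6.13.2.1 says that "statistical summaries and analyses will exclude hypoglycemic events occurring after initiation of a new antihyperglycemic therapy". Nothing is said about stopping person-time at that date. In the same section, severe events needing hospitalization or medical help, or that are life-threatening, go back to the wide window: their analyses "will be conducted using the Safety Analysis Set".

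**Offset.** The general rate model in SAP 6.13 states: "The logarithm of days during the active treatment period will be adjusted as an offset to account for" possibly unequal duration of follow-up. The hypoglycemia model in 6.13.2.1 repeats this: "The logarithm of days during the active treatment period will be adjusted as an offset". 'Active treatment period' is defined nowhere. The nearest defined quantity is duration on study treatment in SAP 6.10: first to last dose, plus 7 days for tirzepatide only.

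**Status.** SAP 6.13.2.1 says the rate may be modelled this way. Protocol 9.4.4.1 says documented symptomatic and severe hypoglycemia will be compared by negative binomial regression. The SAP also commits to a rate per year of exposure by treatment, without defining exposure.

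**The concern.** In a count model with a log person-time offset, the fitted rate is events divided by time only if both refer to the same interval. Here the plan states a counting interval and a person-time interval, and they differ.

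- **Days on drug.** Participants who stop study drug stay in the study and complete all visits (Protocol 7.1), so their later events are counted against time that ended when they stopped. This reading does not fit the exclusion analysis either. Rescue is added on top of study drug (Protocol 8.3.6.2), so days on drug continue after counting has stopped.
- **Study Period II.** This is about 4 weeks short for the safety-set count, because follow-up (with no study drug, SAP 5.1) is included. It is too long for anyone whose events are cut at new therapy in Period II.

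Occurrence of hypoglycemic episodes is a listed safety objective (SAP 4.4), and the comparison is with prandial insulin. If stopping or new-therapy use differs by arm, the error does not cancel in the rate ratio. A difference is plausible: Protocol 6.6.3 and 7.1 contain a stopping rule that applies to tirzepatide only (three or more consecutive doses missed for gastrointestinal intolerance). Stoppers may start another glucose-lowering agent without waiting for the Week 24 rescue threshold (Protocol 6.5).

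**Working it through.** The plan states no event rate, rate ratio or person-time total, so there is no figure to reproduce. Stopping and new-therapy rates below are assumptions; the documents give none by arm.

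**Inputs from the documents:** treatment 52 weeks; follow-up about 4 weeks, so the safety-set window is 52 + 4 = 56 weeks; pooled tirzepatide 591 and lispro 591.

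**1. Events to Week 56.** All participants are assumed followed to Week 56. Compared with an offset matched to the counting window, the arm's rate is multiplied by window / offset.

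Completers: 56/52 = 1.077 in both arms; ratio factor 1.000.

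Days-on-drug offset with a proportion p stopping at week w: mean offset D = (1 - p) x 52 + p x w; factor = 56/D.

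| p | w = 20 | w = 12 |
|---|---|---|
| 5% | 56/50.4 = 1.111 | 56/50.0 = 1.120 |
| 10% | 56/48.8 = 1.148 | 56/48.0 = 1.167 |
| 20% | 56/45.6 = 1.228 | 56/44.0 = 1.273 |

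Rates are therefore 11-27% too high. Rate-ratio factors (tirzepatide versus lispro):

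- 5% vs 5%: 1.000
- 10% vs 5%: 50.4/48.8 = 1.033 to 50.0/48.0 = 1.042
- 20% vs 5%: 50.4/45.6 = 1.105 to 50.0/44.0 = 1.136

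The error in the ratio is thus about 3-14%. The 7 extra tirzepatide days change little: 20% vs 5% at Week 12 becomes 50.0/44.2 = 1.131. With more stopping on lispro the sign reverses: 5% vs 10% at Week 12-24, with the 7 days, gives 0.96-0.97.

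**2. Events cut at new therapy, offset left at 52 weeks.** Counting is taken to end at Week 52 otherwise. With a proportion r starting new therapy at week t, factor = [r x t + (1 - r) x 52]/52.

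| Tirzepatide vs lispro | t | Ratio factor |
|---|---|---|
| 2% vs 2% | 24 | 0.989/0.989 = 1.000 |
| 2% vs 10% | 38; 24 | 0.995/0.973 = 1.022; 0.989/0.946 = 1.046 |
| 0% vs 20% | 38; 24 | 1/0.946 = 1.057; 1/0.892 = 1.121 |
| 10% vs 2% | 38; 24 | 0.978; 0.956 |
| 10% vs 5%, new therapy at stopping | 20 | 48.8/50.4 = 0.968 |
| 20% vs 5%, new therapy at stopping | 12 | 44.0/50.0 = 0.880 |

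The range is about 12% in either direction.

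**3. Simulation.** Negative binomial model, 591 per arm, 100 runs per scenario. Assumed true rates were 2.0 (lispro) and 1.0 (tirzepatide) per year, dispersion 2, and stopping uniform over Weeks 4-40. With events to Week 56 and a days-on-drug offset, the ratio factors were 1.00 (no stopping), 0.99 (5% both), 1.04 (10% vs 5%), 1.10 (15% vs 5%) and 1.16 (20% vs 5%). With the offset matched to the counting window, estimates returned to about 2.0, 1.0 and 0.49-0.51 in every scenario.

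**The case against.** **The term is undefined, so no error is proved.** The stated purpose, allowing for unequal follow-up, is compatible with each participant's time at risk, and programmed that way the bias is zero. This stands as far as it goes: the documents do not show that reported results will be wrong, although a reader might infer it. But time at risk is not what is written, and active treatment does not naturally include a follow-up period without study drug. The SAP does state the window for its time-to-event analyses (first dose to end of participation), so the gap is specific to the rate models.

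**The plan allows other windows.** SAP 6.13 lets selected analyses stop at the 52-week visit, where a Period II offset fits anyone with no early end or new therapy. It also speaks of excluding data after new therapy, which could cover person-time. Neither settles the matter: the analyses using the Week 52 window are not named, and 6.13.2.1 says events.

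**The error may cancel.** It does in the ratio, nearly, when patterns are equal. A reader might infer from the open-label design that they must differ. The documents do not establish that, and Protocol 7.1 describes permanent discontinuation as rare. The bias in each arm's rate remains.

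**Reach is limited.** The SAP makes the hypoglycemia rate model optional, and these analyses have no multiplicity control. Against that, the protocol commits to the negative binomial comparison and the SAP to a rate per year of exposure.

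**Conclusion.** Wrong as written, in the sense that the offset is not matched to the counted window. Confidence is high on the mismatch and moderate on its size, which rests on a constant event rate for completers and on assumed stopping and new-therapy patterns.

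The 11-27% and 3-14% (16% simulated) figures apply to the general rate model and to categories analysed on the full safety set. They do not apply to severe and level 2/severe hypoglycemia under the exclusion. There the ratio may move up or down, depending on which arm starts more new therapy; a reader might infer one direction, but the documents do not support it.

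A reader might also put the rate-ratio error at 9-20% by taking on-treatment rates as the truth (for example tirzepatide constant at 0.4 per year, lispro 4 on drug and 2 off). That overstates it. A matched offset to end of participation estimates the rate regardless of adherence, about 3.8 per year for lispro in that example. Part of the 9-20% is the difference between the two quantities, which correcting the offset would not remove. With 5% stopping in both arms, that comparison still shows a 5-6% error although matched and mismatched offsets give the same ratio.

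Primary and key secondary efficacy and the logistic incidence analyses do not use this offset.

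**What to change.** In SAP 6.13 and 6.13.2.1, replace the offset sentence with: the offset is the log of days at risk in the window in which that analysis counts events. Define days at risk as first dose to the earliest of:

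- the end of that analysis's window (safety follow-up visit or Week 52 visit, as named for the analysis);
- the end of participation;
- the start of new antihyperglycemic therapy, where events are cut there.

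Use the same quantity as the denominator for the rate per year of exposure, and name the analyses that use the Week 52 window.

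The cost is about one sentence in each section and one derived variable per window. No new data are needed, and nothing changes in the efficacy analyses or the testing scheme.

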6.13.2.2. Severe Persistent Hyperglycemia

A summary of initiation of rescue therapy in response to severe, persistent hyperglycemia will be provided by treatment. If there are a sufficient number of episodes, a time-to-first-event analysis for the initiation of rescue therapy will be conducted by treatment using a cox proportional regression model. For patients without an event the “time-to-event” will be time (in days) from first dose to end of study participation (study discontinuation or safety follow-up). A listing of patients initiating rescue therapy will be provided.

6.13.2.3. Pancreatitis

Summaries of adjudicated and investigator-reported pancreatic events will be provided by treatment. Determination of investigator-reported events will be through the pre-defined SMQ search for acute pancreatitis and MedDRA PT of pancreatitis chronic. Detailed searching criteria can be found in [Appendix 1](#). Treatment-emergent adjudicated-confirmed pancreatitis will be considered as AESIs.

6.13.2.3.1. Pancreatic Enzyme Assessment

Observed pancreatic enzyme data (p-amylase and lipase) will be summarized by treatment and nominal visit. The number and proportion of patients with maximum postbaseline pancreatic enzyme values exceeding the following thresholds will be provided by baseline pancreatic enzyme value (\leq upper limit of normal [ULN], $>$ ULN), and treatment: (>1 to ≤ 3) \times ULN, (>3 to ≤ 5) \times ULN, (>5 to ≤ 10) \times ULN, $>10 \times$ ULN.

An MMRM analysis will be used to analyze each pancreatic enzyme with a log transformed (postbaseline measure/baseline measure) response variable and country/pooled country, baseline metformin use (Yes/No), baseline HbA1c category ($\leq 8.5\%$, $>8.5\%$ [≤ 69 , > 69 mmol/mol]), treatment, visit, and treatment-by-visit interaction as fixed effects.

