Each participant will have measurements of pancreatic amylase and lipase, assessed at the central laboratory, as shown in Section 1.3. to assess the effects of the investigational doses of tirzepatide on pancreatic enzyme levels.

Serial measures of pancreatic enzymes have limited clinical value for predicting episodes of acute pancreatitis in asymptomatic participants.²⁹⁻³¹ Thus, further diagnostic follow-up of cases of asymptomatic pancreatic hyperenzymemia, lipase and/or pancreatic amylase 3X ULN or more, is not mandated, but may be performed based on the investigator's clinical judgment and assessment of the participant's overall clinical condition.

Only cases of pancreatic hyperenzymemia that undergo additional diagnostic follow-up and/or are accompanied by symptoms suggestive of pancreatitis will be submitted for adjudication.

Case adjudication and data entry

An independent clinical endpoint committee will adjudicate all suspected cases of acute or chronic pancreatitis. The adjudication committee will also receive data on AEs of severe or serious abdominal pain of unknown etiology to assess for possible pancreatitis or other pancreatic disease.

Study site staff or Lilly staff will enter relevant data for participants with acute or chronic pancreatitis or those with AEs of severe or serious abdominal pain into a specifically designed eCRF page. The adjudication committee representative will enter the results of adjudication into a corresponding eCRF page.

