9.4.4.4. Central Laboratory Measures and Vital Signs

Values and change from baseline to postbaseline values of central laboratory measures and vital signs will be summarized at each scheduled visit. The analysis model to make comparisons among treatment arms, relative to continuous change from baseline values assessed over time will be an MMRM similar to the primary efficacy analysis and with baseline measurement as a covariate. An unstructured covariance structure will model the relationship of within-participant errors.

The percentages of participants with TE abnormal, high, or low laboratory measures at any time will be summarized and compared between treatment arms by using Fisher's exact test. A TE abnormal value is defined as a change from normal value at baseline to a value greater than the high limit at any time during Periods II and III. A TE low result is defined as a change from a value greater than or equal to the low limit at baseline to a value less than the low limit at any time during Periods II and III. High and low laboratory limits will be determined by the central laboratory reference ranges.

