6.10.2. Exposure and Compliance to Insulin

6.10.2.1. Exposure to Insulin

Summary information on total daily dose of insulin glargine (U100) will be reported by visit and by treatment (tirzepatide 5 mg, 10 mg, 15 mg and insulin lispro) for the mITT population during Study Period I and II. A mixed-effect model for repeated measures (MMRM) will be used to analyze the ratio of post-baseline daily insulin glargine doses to baseline daily insulin glargine dose from randomization to Week 52 using the EAS data set. A log transformation will be performed on insulin glargine doses. The model terms will include baseline HbA1c category ($\leq 8.5\%$, $> 8.5\% [\leq 69, > 69 \text{ mmol/mol}]$), baseline metformin use (Yes/No), country/pooled country, treatment, visit, and treatment-by-visit interaction as fixed effects, and log-transformed baseline insulin glargine dose as a covariate. Summary information on total daily dose of insulin lispro (U100) will be reported by visit for the insulin lispro (U100) arm (patients who have received at least one dose of insulin lispro [U100]) during Study Period II.

If applicable, the ratio of total daily dose of insulin glargine (U100) to total daily dose of insulin lispro (U100) will be summarized by visit during Study Period II for the insulin lispro (U100) arm.

Summary information on total daily dose of insulin will be reported during Study Period II.

Unless specified otherwise, all insulin related data will be presented for both units: U and U/kg.

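### The pancreatic enzyme MMRM omits the baseline enzyme covariate that the protocol and the SAP's default safety model include, which costs precision for no stated reason

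*SAP*

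**What the plan says.** SAP 6.13.2.3.1 gives pancreatic enzymes their own model: "An MMRM analysis will be used to analyze each pancreatic enzyme with a log transformed (postbaseline measure/baseline measure) response variable". The terms are country or pooled country, baseline metformin use, the two-level HbA1c category, and finally "treatment, visit, and treatment-by-visit interaction as fixed effects". The sentence ends there.

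The comparable models in the two documents read differently:

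- **SAP 6.13, default for continuous safety parameters.** It opens "Unless specified otherwise, differences among treatment mean changes from baseline in continuous safety parameters at all scheduled visits will be assessed via an MMRM", and its list of terms closes with "as fixed effects, and baseline value of the safety parameter as a covariate".
- **Protocol 9.4.4.4, central laboratory measures and vital signs.** The model "will be an MMRM similar to the primary efficacy analysis and with baseline measurement as a covariate". Amylase and lipase fall under it, since protocol 8.3.6.3 says: "Each participant will have measurements of pancreatic amylase and lipase, assessed at the central laboratory".
- **SAP 6.13.3, vital signs.** The model includes the baseline value of the dependent variable.
- **SAP 6.10.2.1, glargine dose.** This is also a log-transformed ratio to baseline analysed by MMRM, and it keeps "log-transformed baseline insulin glargine dose as a covariate".

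Neither 6.13.2.3.1 nor the SAP revision history explains why the enzyme model differs.

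**The concern.** Dividing by baseline does not adjust for it in the way a covariate does. On the log scale the response is log(post) minus log(baseline), so leaving out log baseline is the same as fixing its slope at 1. Enzyme values that are high at baseline partly by chance tend to fall back. That regression to the mean then sits in the error term instead of being explained.

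Two things follow. The interval for the treatment ratio is wider than it need be unless the true slope is 1. In addition, part of any chance baseline difference between arms passes into the estimated ratio. Pancreatitis is a special safety topic, and these measurements are taken to describe what tirzepatide does to enzyme levels, so the estimate should be as precise as the data allow.

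**Working it through.** The plan states no precision or power figure for this analysis, so there is none to reproduce.

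**Inputs.** The response and terms are those of SAP 6.13.2.3.1. The planned numbers are 591 pooled tirzepatide against 591 insulin lispro (SAP 5.2). The schedule of activities has both enzymes measured at Visit 6 (baseline) and at weeks 12, 24, 40 and 52. The baseline–postbaseline correlation ρ and the log-scale SDs are not in the documents; they are assumed and varied below.

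**Formulae, at one visit.** Let s0 and s1 be the log-scale SDs at baseline and postbaseline. The variance of the treatment contrast is proportional to

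- without the covariate: s0² + s1² − 2ρ·s0·s1
- with log baseline: s1²(1 − ρ²)

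The slope of log post on log baseline is β = ρ·s1/s0. The first variance is never smaller than the second, and the two are equal only when β = 1.

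**Equal SDs.** With s0 = s1 the ratio of adjusted to unadjusted variance is (1 − ρ²)/(2(1 − ρ)) = (1 + ρ)/2.

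| ρ | Variance ratio | SE ratio | SE reduction from adding log baseline | Excess CI width without it |
|---|---|---|---|---|
| 0.4 | 0.70 | 0.837 | 16% | 19.5% |
| 0.6 | 0.80 | 0.894 | 11% | 11.8% |
| 0.8 | 0.90 | 0.949 | 5% | 5.4% |
| 0.9 | 0.95 | 0.975 | 3% | 2.6% |

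**Unequal SDs.** Let k = s1/s0. The excess width is √[(k² + 1 − 2ρk)/(k²(1 − ρ²))] − 1.

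| k | ρ = 0.5 | ρ = 0.7 | ρ = 0.8 | ρ = 0.9 |
|---|---|---|---|---|
| 0.8 | 32.3% | 26.2% | 25.0% | 28.2% |
| 1.0 | 15.5% | 8.5% | 5.4% | 2.6% |
| 1.25 | 5.8% | 1.0% | 0.0% | 2.6% |

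The zero arises because β = 0.8 × 1.25 = 1.

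**Repeated-measures check.** A four-visit model with unstructured covariance was simulated with 591 against 591, complete data, the same correlation throughout, equal SDs and 300 runs. It was fitted with and without a common baseline slope. Excess interval width was 15.3% (ρ 0.5), 8.5% (0.7), 5.3% (0.8) and 2.5% (0.9), in line with the formula. Both estimates averaged the true difference, so neither model was biased.

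**Baseline imbalance.** If the arms differ by Δ in mean log baseline, the unadjusted contrast is shifted by (β − 1)Δ. With equal SDs and ρ = 0.6 that is −0.4Δ. The standard error of Δ with 591 per group is s0·√(2/591) = 0.058·s0, so a typical shift is 0.4 × 0.058 = 0.023·s0.

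**The case against.** The strongest reply is that nothing has been dropped. SAP 6.13 lists fixed effects and the covariate separately, and 6.13.2.3.1 lists only fixed effects. The enzyme section is also silent on the estimation method and the covariance structure, which must come from the default; perhaps the covariate does too. That leaves some ambiguity. But where the SAP writes out a model of this kind in its own section, as for vital signs and glargine dose, it names the baseline covariate, and here it does not. A programmer following the text would leave it out.

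A second reply is that departures are permitted. SAP 6.13 applies unless otherwise specified, and both documents allow non-principal changes of method with a justification in the SAP or the clinical study report. That is correct procedurally. The report is not available here and may give a reason; the SAP gives none.

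Third, the size is not known. The (1 + ρ)/2 result needs equal variances, and with a larger postbaseline SD the gain may be close to zero. This stands as a limit on magnitude, not on direction.

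Fourth, the analysis is minor. Amylase and lipase are not among the listed safety objectives, and protocol 8.3.6.3 itself gives serial enzyme values little predictive use in people without symptoms. The threshold table in 6.13.2.3.1 is already split by baseline category, and no hypothesis or alpha is attached to the MMRM. Only part of any imbalance is carried through, and that part is small. All of this is fair and keeps the point at the lowest severity. None of it is a reason to prefer the less precise model.

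**Conclusion.** The point holds as a minor one. Read literally, SAP 6.13.2.3.1 omits a covariate that protocol 9.4.4.4 specifies and that the SAP's own default and its other log-ratio model include, and it does not say why.

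The cost is precision. Under equal log-scale SDs and an assumed correlation of 0.5 to 0.9, intervals are about 3% to 16% wider than necessary. With a postbaseline-to-baseline SD ratio of 0.8 the excess is 25% to 32% over the same range; with a ratio of 1.25 it is 0% to 6%. These figures are illustrative, because the documents supply neither the correlation nor the SDs. Randomisation keeps the treatment contrast unbiased under both models. The analysis lies outside type 1 error control, so no primary or key secondary conclusion changes.

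**What to change.** In SAP 6.13.2.3.1, add the log-transformed baseline value of the enzyme as a covariate, in the form already used for glargine dose in 6.10.2.1. State in the same place that the estimation method and covariance structure follow 6.13. This brings the section into line with SAP 6.13 and protocol 9.4.4.4 and settles the ambiguity on either reading.

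The cost is one model term. Baseline enzymes are collected at Visit 6 and are already needed as the denominator of the response, so no new data are required. It is a free improvement.
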